Major Outcomes	
 
• Safety: severe Potassium or Bicarbonate abnormalities, or unscheduled hemodialysis (HD) or hospitalization for hyper/hypokalemia or acid/base abnormalities in absence of missed treatment.
 
• Tolerability: treatment adherence
 
• Efficacy: mean and standard deviation of the change in duration of clinically significant arrhythmias per month
 
• Feasibility: recruitment rate, retention
 

Statistical Methodology	
A balanced, uniform crossover design will be used with randomization stratified by site in blocks of 4.
 
Adherence will be estimated as % (95% CI) of sessions without protocol deviation. Comparison of adherence percentage pre- vs. post-interim analysis of adherence will be made using linear regression with time period as an independent variable. Exploratory analyses will assess association of adherence with site, dialysis shift (1st-3rd), and dialysis day-of-the-week schedule (Monday/Wednesday/Friday or Tuesday/Thursday/Saturday).
 
Safety will be assessed by calculating the incidence rate for serious AEs and intervention-specific complications. Comparisons of incidence rate between interventions will utilize Poisson regression adjusted for randomization scheme and site.

Funding	
National Institutes of Health National Heart, Lung and Blood Institute R34 NHLBI Clinical Trial Pilot Studies (R34)  https://grants.nih.gov/grants/guide/pa-files/PAR-16-037.html

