## II. Specific Aims

Overview of Trial Design—The overall goal for these trials is to provide the data necessary for the design of definitive clinical trials. Specifically, we aim to test recruitment feasibility, the feasibility of POC electrolyte measurement and POC-directed management of the dialysis prescription, and to provide preliminary estimates of effect size with manipulation of UF rate, dialysate K, and dialysate HCO3. We will perform two related, randomized cross-over trials; Study A- dialysate interventions trial, consisting of 2 dialysate potassium interventions and 2 dialysate bicarbonate interventions (4 total cross-over interventions); and Study B-ultrafiltration rate intervention trial, consisting of 2 separate ultrafiltration rate strategies.

The central hypothesis underlying Study A and Study B is that the risk of clinically significant arrhythmias in HD patients can be reduced by altering components of the dialysis prescription.

**Aim 1—To test the feasibility and safety of POC-guided dialysate prescription adjustment and the feasibility of limiting UF rate in HD patients.** The current studies will pilot our educational strategies and the dialysate potassium, dialysate bicarbonate and UF intervention strategies to test their feasibility in a multi-center setting. They will test the hypothesis that  $\geq 80\%$  adherence with proposed interventions is feasible, and that the safety need for unscheduled dialysis or severe abnormalities in potassium and bicarbonate will be minimal.

**Aim 2—To assess recruitment feasibility and retention rate for trials combining ILR insertion to monitor arrhythmia and interventions using POC-guided dialysis prescription or UF rate manipulation.** Screen failures and retention rates will be captured and analyzed. Whether recruitment rates  $\geq 1$  patient per month and retention rate  $> 90\%$  are achievable in each study will be tested.

**Aim 3—To refine effect estimates of the change in monthly CSA duration during Study A (dialysate potassium intervention to maximize vs. minimize intradialytic potassium removal) and Study B (aggressive vs. conservative ultrafiltration rate).** Refining estimates of change in CSA with each pair of interventions will provide key information necessary for design of definitive trials. Whether CSA decreases with minimization of potassium removal, alkalosis limitation and UF rate minimization will be tested.

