**Adherence Endpoints**—Adherence will be assessed for each of the 4 dialysate interventions (K removal minimization vs. maximization, acidosis vs. alkalosis avoidance) as the % of sessions in which POC testing is completed and the dialysate is adjusted according to the algorithm. For the UF trial, it will be assessed as the % of sessions in which the mandated UF rate is delivered. We hypothesize that 90% adherence is achievable. HD staff will be anonymously surveyed once 3 subjects have completed 1 month of each trial and once 6 patients have completed each trial. A questionnaire will identify the impact of time constraints, patient refusal, algorithm complexity, inadequate training on POC devices, clinical concerns, or other factors on protocol adherence. Face-to-face review with HD staff will facilitate identification of other barriers. Where addressable factors are identified, they will be corrected for remainder of the trials. Since the overall goal is to assess implementation feasibility, secondary analyses will compare pre- and post-correction adherence in addition to estimating overall adherence. This adaptive plan will facilitate identification of best practices and ensures that estimates represent the feasibility of subsequent protocols to be implemented after incorporating lessons learned in the pilot experience.

**Secondary Feasibility Measures**—POC electrolyte measurements will be compared with usual care monthly labs to assess accuracy of POC testing. An additional metric that will be used to determine the impact of POC testing on trial design will be the percent of sessions in which the POC-guided dialysate prescription differs from a hypothetical prescription in which the choice of dialysate is based solely on the once-monthly lab.

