**Safety Endpoints**—The primary safety endpoint will include the incidence of all serious adverse events and intervention-specific complications: a) Potassium Intervention—severe K abnormalities ( $K \geq 6.5$  or  $\leq 3.0$  mEq/L), or unscheduled HD or hospitalization for hyper/hypokalemia in the absence of a missed treatment; b) Bicarbonate Intervention—severe  $HCO_3$  abnormalities ( $HCO_3 < 20$  or  $> 32$  mEq/L) or unscheduled HD or hospitalization for acid base abnormalities in the absence of a missed treatment; c) Ultrafiltration Intervention—Unscheduled HD or hospitalization for volume overload. Secondary safety endpoints include the occurrence of CSAs requiring further management, all-cause mortality, cardiovascular mortality, and hospitalization.

**Recruitment Feasibility (Aim 2)**—Recruitment feasibility will be analyzed by testing whether an overall recruitment rate of 1 patient/month is achieved in each trial (1-sample test). This is a critical metric, as a large-scale trial cannot be feasibly completed in a practical number of centers if between 0.5-1 patient/month cannot be enrolled. This rate represents a minimum criterion for feasibility.

The percent of screened patients enrolled will be calculated as a secondary feasibility measure to assess the size of the necessary screening pool. Reasons for non-enrollment (vis-a-vis inclusion and exclusion criteria and patient and physician preferences) will be assessed to determine the potential for protocol modification to improve recruitment. Subject retention will be calculated as the percentage of enrolled patients completing the trial. Retention rates of 90% will be considered the benchmark for feasibility.

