**Effect Estimates (Aim 3)**—Estimating the mean and standard deviation (SD) of the change in duration of clinically significant arrhythmia (CSA) per month is critical for power and sample size calculation and planning definitive studies. The total monthly duration of CSA (in minutes) will be utilized as the primary efficacy endpoint in comparing each pair of interventions (K removal maximization vs. minimization, acidosis vs. alkalosis avoidance, aggressive vs. conservative UF). In the event of incomplete follow-up, CSA duration will be indexed to follow-up time. CSA will be defined on the basis of arrhythmias likely to lead to SCA or serious morbidity and mortality and will include AF, asystole  $\geq 3$  seconds, bradycardia  $\leq 40$  beats per minute lasting  $\geq 6$  seconds, and sustained VT  $\geq 130$  beats per minute lasting  $\geq 30$  seconds. CSA's will be adjudicated by study electrophysiologists.. Currently, no data exists on the expected impact of the interventions on CSA duration, but given a mean duration of CSA in MiD of  $356 \pm 1765$  minutes, a sample size of 20 subjects provides 80% power for detection of change in CSA duration of 140 minutes/month given within-subject correlation of 0.9, 370 minutes for within-subject correlation of 0.7, and 470 minutes if within-subject correlation is 0.5.

**Statistics and Analysis**—A balanced, uniform crossover design will be used with randomization stratified by site in blocks of 4.

**Adherence** will be estimated as % (95% CI) of sessions without protocol deviation. Comparison of adherence percentage pre- vs. post-interim analysis of adherence will be made using linear regression with time period as an independent variable. Exploratory analyses will assess association of adherence with site, dialysis shift (1st-3rd), and day (Monday/Wednesday/Friday or Tuesday/Thursday/Saturday).

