**Safety** will be assessed by calculating the incidence rate (complications per unit follow-up time) for serious adverse events and intervention-specific complications. Comparisons of incidence rate between interventions will utilize Poisson regression adjusted for randomization scheme and site. Exploratory analyses will assess age, sex, race, mean intra-dialytic weight gain, potassium concentration and HCO3 concentration in month prior to randomization on the incidence of adverse events. Given the pilot nature of the trials and major goal of informing feasibility estimates for definitive trials, P<0.05 will be considered significant in all safety analyses. No adjustments will be made for multiple comparisons given the pilot nature of the studies.

**Efficacy** estimates for Aim 3 will utilize the mean duration of CSA as the primary outcome. In the event of incomplete follow-up, this will be indexed to duration of follow-up time (e.g. minutes per day). Change in CSA duration between interventions will be analyzed using mixed effects linear regression with terms for treatment, research site, period, sequence, and random effects for subjects. Primary outcomes for the dialysate trial will compare CSA during potassium maximization vs. minimization, and acidosis vs. alkalosis avoidance. For the UF trial, aggressive vs. conservative UF will be compared. Physiologically, the washout period of 1-week in the dialysate trial and 1 weekend in the UF trial is sufficient to avoid the possibility of carryover effects. Potential for sequence effects is minimized by a design with uniform sequences (all treatments appear once within each sequence). Potential for carryover and randomization sequence effects will be analyzed by including terms for sequence and their interaction with treatment in the models.

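### The adherence interval and the pre/post regression name no patient term, although each of 20 patients contributes 12 to 48 sessions

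*Combined protocol and SAP*

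**What the plan says.** Section VI, Statistics and Analysis, says that adherence "will be estimated as % (95% CI) of sessions without protocol deviation". The comparison before and after the interim look at adherence is made "using linear regression with time period as an independent variable". The Study Summary repeats this ("Comparison of adherence percentage pre- vs. post-interim analysis of adherence will be made using linear regression"). No interval method, unit of analysis, patient term or robust variance is given. Site, shift and dialysis day appear only as exploratory factors.

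The efficacy paragraph of the same section does handle repeated data from one patient, using "mixed effects linear regression with terms for treatment, research site, period, sequence, and random effects for subjects".

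Two adherence levels are mentioned. Aim 1 in section II tests whether at least 80% "adherence with proposed interventions is feasible". Adherence Endpoints in section VI says "We hypothesize that 90% adherence is achievable". Neither figure is given a role. The recruitment and retention figures are: "This rate represents a minimum criterion for feasibility" and "Retention rates of 90% will be considered the benchmark for feasibility".

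Adherence Endpoints also sets two staff surveys, one after three subjects finish a month and one after six patients finish a trial, with corrections to follow. It calls the pre/post comparison secondary.

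**The concern.** Sessions from one patient are unlikely to be independent. Adherence Endpoints itself lists patient refusal among the possible barriers, and a patient who refuses once may refuse again. A binomial interval on pooled sessions treats 240 sessions from 20 patients as 240 separate observations.

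The analyses are exploratory, so what Aim 1 delivers to the definitive trials is the adherence estimate and its interval. If the interval is too narrow, those trials will be planned with more confidence than the data allow. The pre/post comparison carries a further risk. Entry is staggered, so the sessions before and after a correction come largely from different patients, and a session-level regression can credit the correction with a difference that is only between patients.

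**Working it through.** The plan states no interval width or power for adherence, so there is no figure of its own to reproduce.

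**Inputs from the documents (section V).** 20 patients per trial; 12 scheduled sessions per intervention; 2 x 12 = 24 sessions per Study B patient; 4 x 12 = 48 per Study A patient. Pooled totals are 240, 480 and 960. These are scheduled counts; a patient may receive as few as 6 sessions per intervention.

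**Assumptions.** The within-patient ICC is not in the documents. I use 0.05 to 0.30, with 0.01 as mild clustering. True adherence is set at 90%.

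**Half-width.** With *m* sessions per patient, the independent-session half-width is 1.96 x sqrt(0.9 x 0.1 / 20*m*). With clustering it is multiplied by sqrt(DE), where DE = 1 + (*m* - 1) x ICC. For *m* = 12:

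- Independent: 1.96 x sqrt(0.09/240) = 3.8 points.
- ICC 0.05: DE = 1 + 11 x 0.05 = 1.55, giving 3.8 x 1.245 = 4.7.
- ICC 0.30: DE = 1 + 11 x 0.30 = 4.30, giving 3.8 x 2.074 = 7.9.

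All three use the normal quantile, so they compare like with like.

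**Coverage.** This comes from beta-binomial simulation (20 patients, 40,000 replicates), using the simple Wald interval on pooled sessions.

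| Sessions per patient | Half-width, independent | Half-width, ICC 0.05 to 0.30 | Coverage, ICC 0.05 to 0.30 | Coverage, ICC 0.01 |
|---|---|---|---|---|
| 12 (one intervention) | 3.8 | 4.7 to 7.9 | 87 to 63% | 92% |
| 24 (Study B) | 2.7 | 3.9 to 7.5 | 82 to 50% | 92% |
| 48 (Study A) | 1.9 | 3.5 to 7.4 | 71 to 37% | 89% |

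Part of the shortfall at 12 sessions belongs to the Wald formula, which covers 93.9% with no clustering. A Wilson interval covers 94.9% at ICC 0.01, but still falls to 68% at ICC 0.30.

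**Example.** Suppose 204 of 240 sessions (85%) are adherent. The independent interval is 85 ± 1.96 x sqrt(0.85 x 0.15/240), or 80.5 to 89.5%. It appears to clear 80% and exclude 90%. Multiplying the half-width by sqrt(DE) gives 79.4 to 90.6% at ICC 0.05 and 75.6 to 94.4% at ICC 0.30, which do neither.

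**Pre/post comparison.** I simulated session-level regression with no true change (20,000 replicates), assuming evenly spaced entry and a correction that takes effect at the survey. Results for Study A at the second survey:

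| Entry rate | Patients wholly pre / straddling / wholly post | False positives at ICC 0.05, 0.10, 0.20, 0.30 |
|---|---|---|
| 1 per month (the plan's target) | 6 / 4 / 10 | about 26, 38, 51, 59% |
| 2 per month (assumed) | 6 / 8 / 6 | about 22, 35, 48, 56% |

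At ICC 0.01 the rate is about 10%. If every patient straddles the change evenly, there is no inflation (2 to 5%). If the regression uses one percentage per patient per phase, the rate is 1 to 8% for ICC 0.05 to 0.30 and 4 to 17% at ICC 0.01.

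**The case against.** The strongest objection is that no error has been shown. A reader might infer that the plan treats sessions as independent, but it does not say so. The phrase about sessions defines the proportion, not its variance. The adherence percentage in the pre/post sentence may well mean per-patient values, which largely removes the problem. This stands, and every figure above is conditional on it. It does not remove the point: the plan names a subject effect for arrhythmia and none for adherence, and the result depends heavily on which reading is followed.

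The ICC is also assumed. Several of the listed barriers (time, algorithm complexity, device training) act on staff or the unit rather than the patient, and nothing in the documents supports a value near 0.30. That too stands. At ICC 0.01 the effect is small for one intervention, though coverage over Study A is still about 89%.

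The pre/post comparison is secondary in an exploratory pilot, so it adds little weight.

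A reader might also infer that 80% and 90% contradict each other. They do not: 90% satisfies at least 80%, and the two can be a floor and an expectation. An observed 85% meeting one and missing the other is what that pairing would mean, and the plan ties no decision to either figure. All that is missing is a statement of which is which.

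**Conclusion.** The point holds as a gap in specification with a real consequence if the text is run literally on sessions. In that case the adherence interval is too narrow. At 90% adherence and an assumed ICC of 0.05 to 0.30, coverage is about 87 to 63% per intervention and 71 to 37% over Study A, and the half-width per intervention should be 4.7 to 7.9 points rather than 3.8. Study A false positives at the second survey are roughly 25 to 60% over that ICC range, with little or no inflation if patients straddle the change evenly. The ICC, the entry pattern and the timing of corrections are assumptions. The change is worth making because it is cheap and protects the main product of Aim 1. The 80% and 90% labels are a minor clarification.

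**What to change.** In the adherence paragraph of section VI and in the Study Summary:

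- State the unit of analysis and name the patient as the cluster.
- Compute the interval for the percentage of sessions itself (the marginal scale). One option is a patient-clustered logit or GEE interval with small-sample correction and t on 19 degrees of freedom (simulated coverage 93 to 95%). A simpler one is a t interval on patient-level percentages (about 89 to 94%).
- Do not back-transform the intercept of a logistic mixed model without averaging over patients. It describes the typical patient and overstates the session percentage: with normal random effects and ICC 0.05 to 0.30 on the probability scale, it gives 91.7 to 97.0% when the true figure is 90%.
- Add a patient random intercept to the pre/post linear model (simulated false positives 3 to 5%). A plain cluster-robust standard error is not enough at the first survey (14 to 24%), where only 3 or 4 patients contribute earlier sessions.

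Minor clarifications: say in Aim 1 and in Adherence Endpoints which of 80% and 90% is the minimum and which the expectation. Study B adherence may also be reported by UF strategy, as Study A's is by intervention; that would need a statement of what counts as a deviation in unrestricted weeks.

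The cost is wording only, with no new data. The intervals will be wider and, with 20 patients, may not separate 80% from 90%. The pre/post comparison will be imprecise if the correction comes early.

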**Ultrfiltration (UF) Rate and Arrhythmia Risk**—Maintaining normovolemia is a cornerstone of dialysis therapy and is achieved by adjusting fluid removal rates to reach a stable post-dialysis weight. Large interdialytic fluid gains are common and result in high prescribed UF rates. When UF rates exceed the rate of vascular space refilling from the periphery, cardiac filling and myocardial perfusion is impaired leading to adverse outcomes. Multiple studies suggest that high UF rates are associated with mortality. In one study of 22,000 patients, mortality was significantly higher with UF rates  $\geq 10$  mL/hr/kg (RR 1.09,  $P=0.02$ ). A secondary analysis of the HEMO trial similarly found an increase in CV (HR 1.59, 95% CI: 1.29-1.96) or all-cause mortality (HR 1.20, 95% CI: 1.03-1.41) at UF rates  $>13$  ml/hour/kg while mortality rates increased at UF rates  $>10$  mL/hr/kg when analyzed as continuous variable. In the MiD study, an increase in intra- and peri-dialytic clinically significant arrhythmias was also noted with higher UF rates (**Figure 4**). Although these data underlie recent recommendations to incorporate UF rate as a dialysis quality measure, no randomized data comparing different UF rates on outcomes exist, and multiple factors are likely to cloud associations with UF rates in observational studies. The two trials proposed under this protocol will be the first to provide randomized data on modifications of the UF rate on risk of serious arrhythmias. Furthermore, due to the need to get patients to a dry weight and limited resources to extend dialysis time or add additional sessions, the standard of care remains to dialyze patients with large intradialytic fluid gains using UF rates  $\geq 10$  L/kg. In short, despite recent efforts to adopt UF limitation as a quality measure, it has not achieved acceptance as the prevailing standard of care.

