Study procedures ensure testing of electrolytes at each session (3x/week) in contrast to a frequency of as little as 1x/month in routine practice. Severe electrolyte abnormalities will thus be recognized earlier with study patients than in routine practice. Similarly, POC testing will ensure that the dialysis prescription will be adjusted according to the ambient potassium or bicarbonate at that dialysis session. In routine practice, follow-up testing at outpatient dialysis units typically has a turn-around time of hours (stat testing) or days (routine lab draws) which makes appropriate adjustment of the dialysis prescription unfeasible. Thus, study procedures may actually lower the risk of severe electrolyte abnormalities or risk of complications from those abnormalities. However, significant inaccuracy in the point of care testing results could modify the associated risks.

To further mitigate risk, patients with severe abnormalities in potassium ( $K>6.5$  or  $<3.0$ ) or bicarbonate ( $<20$  or  $>32$ ) will temporarily come off therapy and be treated off-protocol at the discretion of their clinician.

**Study B UF algorithms** are designed to either limit UF rates to  $\leq 10$  mL/kg/hour or to allow UF rates  $\geq 13$  mL/kg/hour. As discussed in the research summary, there is significant equipoise regarding the risk/benefit ratio of either strategy, as the use of high UF rates minimizes the risk of volume overload at the expense of rapid fluid shifts, whereas limiting UF rate minimizes the risk of rapid fluid shifts at the expense of increasing the risk of volume overload. Both strategies are routinely employed in clinical care. Thus, it is again unclear whether research-related risks are materially different than those in routine practice. As described in the Research Plan, subjects will cross over weekly between the unlimited and restricted UF treatments, thereby allowing removal of excess fluid accumulated during the restrictive week during the subsequent, unlimited week. This will limit any excessive fluid gains to a maximum of a few liters over the course of the restricted UF week thereby limiting the possibility of volume-related complications in the event patients fail to self-regulate intake of salt and water. Safety, will be further ensured because patients who show signs of significant volume overload will have the

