potential to schedule an extra UF session as needed (outside of the protocol) in the event that symptoms of volume overload are intolerable. Lastly, all hospitalizations for myocardial infarction or heart failure will be reviewed by the DSMB. Events will be reviewed within 1 week in order to assess for potential relatedness, need to halt the study or revise the protocol, or need for ad-hoc review by the DSMB of un-blinded data in order to protect research subjects.

**iv. Breach of confidentiality:** Inadvertent release of information about medical history, laboratory information, or test results poses a psychological/financial risk. To maintain confidentiality and minimize risks to privacy, data will be de-identified and stored using a unique, coded study identifier for each subject. All data will be stored on password-protected servers and will be protected behind medical center fire walls and with contemporary virus software. Only the study staff will have access to the network drive. The only individually identifiable data that will be collected are names, medical record numbers, addresses, and contact phone numbers. These data are required for patient follow-up and for use during registration in the hospital information systems prior to ILR insertion. The file linking the study ID and personally identifiable information will be kept by the PIs in a similarly secure network drive location with access limited to the PIs and study coordinators or staff with responsibility for contacting patients. This file will be accessed only as necessary for patient follow-up or safety concerns. All other recorded data will be identified by study number only, and will be housed separately from data containing patient identifiers. Only the principal investigator (or personnel responsible for contacting patients) will have access to cross-reference the files. Sharing of data between Duke and NYU will involve only de-identified data. REDCAP or other electronic data capture instruments will be used to record study data and create a single, study database.

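### Study B's UF-specific safety item counts volume overload but has no counterpart for the harms of rapid fluid removal

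*Combined protocol and SAP*

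**What the plan says.** Section VI, Safety Endpoints, has two parts: "The primary safety endpoint will include the incidence of all serious adverse events and intervention-specific complications". The intervention-specific part differs by trial.

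- **Potassium:** K of 6.5 or above or 3.0 or below, or "unscheduled HD or hospitalization for hyper/hypokalemia in the absence of a missed treatment".
- **Bicarbonate:** values below 20 or above 32, or unplanned dialysis or admission for an acid-base problem.
- **UF:** "Ultrafiltration Intervention—Unscheduled HD or hospitalization for volume overload".

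The same paragraph adds: "Secondary safety endpoints include the occurrence of CSAs requiring further management, all-cause mortality, cardiovascular mortality, and hospitalization". Under Statistics and Analysis, incidence rates of serious adverse events and intervention-specific complications are compared by Poisson regression. P<0.05 counts as significant and there is no multiplicity adjustment.

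Section VII (Study B UF algorithms) sets out the trade-off behind equipoise. On the restricted strategy it says that "limiting UF rate minimizes the risk of rapid fluid shifts at the expense of increasing the risk of volume overload". On the opposite strategy its statement is that "the use of high UF rates minimizes the risk of volume overload at the expense of rapid fluid shifts". Section I gives the mechanism for the harm of fast removal: "When UF rates exceed the rate of vascular space refilling from the periphery, cardiac filling and myocardial perfusion is impaired leading to adverse outcomes".

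Section V has the two UF conditions alternate weekly, so that fluid left by a restricted week is cleared in the next unrestricted one. Section VI takes one weekend as adequate washout.

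**The concern.** The plan names a harm for each UF strategy but builds only one of them into the UF-specific endpoint. A safety comparison between two strategies with opposite expected harms is informative only if both harms can be counted on similar terms. Here an overload event can count without being serious, because unscheduled dialysis is enough. A rapid-removal complication that is not serious is not counted anywhere in the Poisson comparison.

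The pilot exists to inform definitive trials, and Section VI calls the safety of the interventions critical to scaling them up. A UF-specific rate that sees one kind of harm could make restriction look less safe than a balanced count would, whatever its P-value. Restriction is the strategy Aim 3 hypothesizes to reduce arrhythmia.

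**Working it through.** The plan gives no figure for this endpoint, so there is none to reproduce. The check compares definitions, followed by arithmetic on what the component could show. Values marked assumed are not in the documents.

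**1. Definitions side by side**

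| Item | One direction | Other direction |
|---|---|---|
| Potassium | high K | low K |
| Bicarbonate | low HCO3 | high HCO3 |
| UF | volume overload (restricted UF) | none (rapid shifts, unrestricted UF) |

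**2. What enters the Poisson comparison** (taking serious in its usual regulatory sense)

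| Event | Serious | Not serious |
|---|---|---|
| Overload | yes | yes, if it leads to unscheduled dialysis |
| Rapid removal | yes, as an SAE | no |

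To illustrate, assume 10 background SAEs per condition, 4 countable overload events under restriction and 4 rapid-removal complications under unrestricted UF, of which 2 are serious.

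- UF-specific component: 4 v 0.
- Both parts together: (10+4)/(10+2) = 1.17, restricted over unrestricted, although the true numbers of complications are equal.
- If all 4 rapid-removal events were serious: 14/14 = 1.00.

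**3. Can the all-SAE part point either way?** Ratio = (b+v)/(b+h), with b background, v overload and h rapid-removal SAEs per condition. With b = 10 (assumed):

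- v=4, h=0: 14/10 = 1.40
- v=4, h=4: 14/14 = 1.00
- v=2, h=4: 12/14 = 0.86

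It can.

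**4. Is the tilt of the UF item certain?** Suppose only restriction causes overload and a share f of those events presents in the following unrestricted week. Counted by week of onset and ignoring the end of the schedule, the observed ratio of restricted to unrestricted is (1−f)/f.

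| f | 0 | 0.25 | 0.5 | 0.6 | 0.75 |
|---|---|---|---|---|---|
| ratio | infinite | 3.0 | 1.0 | 0.67 | 0.33 |

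The item turns against unrestricted UF once more than half of the events present late. The plan states no attribution rule.

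**5. How much can the comparison resolve?** Twenty subjects × 4 weeks = 80 patient-weeks per condition if complete (80×7/365.25 = 1.53 patient-years). With equal exposure, a two-sided exact test conditional on the total, ignoring within-subject correlation, needs at least 6 v 0: 2×0.5⁶ = 0.031. A split of 8 v 1 or 10 v 2 gives 0.039. At assumed overload rates of 0.02, 0.05 and 0.10 per restricted patient-week, expected counts are 1.6, 4 and 8. The chance of 6 or more events is 0.6%, 21% and 81%.

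**The case against.** A reader might infer that Study B's safety comparison can only favour unrestricted UF. The documents do not support that. The UF item is one part of an endpoint that also counts every serious adverse event under both conditions. Admissions for infarction or arrhythmia, and deaths, would ordinarily be serious. Mortality, hospitalization and arrhythmias needing management are secondary safety endpoints. Arrhythmia, the main harm hypothesized for high UF, is the primary efficacy endpoint. Section VII adds that "all hospitalizations for myocardial infarction or heart failure will be reviewed by the DSMB", and Section IX sends deaths and arrhythmia admissions to the DSMB. All of this stands. None of it counts a rapid-removal complication that is neither serious nor an arrhythmia.

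A reader might also take the direction of the tilt as certain. Step 4 shows that weekly alternation with one weekend of washout can reverse it.

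A third inference is to size the bias from the UF contrast. At the entry level of 13 mL/kg/h needed and 10 allowed, recovering the shortfall over three equal sessions gives 13+3 = 16 v 10. That describes separation in UF rate, not bias in an endpoint. It also assumes every session needs exactly 13, whereas entry requires at least 13 in only six or more sessions of the prior month.

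It is also fair to say that unrestricted UF is labelled standard of care, so watching for the foreseeable added risk of restriction is defensible, and a higher overload rate would be a true finding about overload. Section VI calls the analyses exploratory, and step 5 shows that a significant result needs a lopsided split. These points limit the consequence. They do not make an overload-only rate a balanced comparison of the two strategies.

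**Conclusion.** The point holds for the UF-specific component only. That component is one-sided where its potassium and bicarbonate counterparts are not, and it admits non-serious overload events while non-serious rapid-removal events are left out. It is expected to tilt against restriction.

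The size cannot be obtained from the documents, which give no event rates. The 1.17 in step 2 is an illustration on assumed counts. The expected direction assumes that most overload is recorded in the restricted week that caused it. The wider safety comparison can go either way. This is a moderate and inexpensive improvement to an endpoint definition, and it does not invalidate the trial.

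**What to change.** In Section VI, Safety Endpoints, and in its analysis paragraph:

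1. Add a prespecified rapid-removal complication item to the UF component. The clinical team should set its definition, using the dialysis treatment records already reviewed at the Study B visits (Section V).
2. Report overload and rapid-removal complications separately by UF condition, and interpret them together beside the all-SAE rate.
3. State how an event is attributed to a condition, for example by week of onset, with a sensitivity analysis that moves overload events to the preceding restricted week. The rule should cover a first unrestricted week, which has no restricted predecessor, and events just after a final restricted week 12.
4. State whether the extra off-protocol UF session allowed in Section VII counts as unscheduled dialysis.
5. Add the UF items to the safety outcome in the Study Summary, which now lists only electrolyte and acid-base events.

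Post-dialysis weight minus target weight should not serve as a safety measure: Section V expects restricted weeks to miss the target, so it differs by design.

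The cost is added wording and extra abstraction. The plan does not list which treatment-record fields are captured, so availability needs confirming. Charting is by unblinded dialysis staff, a limit the existing unscheduled-dialysis item shares. No UF rate or clinical rule changes.
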